9.10.4 Data Monitoring Committee

An external, independent DMC will be comprised of experts in MDS not involved in the ACE-536-MDS-002 study, and an independent Statistician, and may include additional ad hoc members. Representatives of the sponsor may attend the open session of DMC meeting but will not be present during the closed sessions of DMC meetings.

During the course of the study, the DMC will review the safety data regularly as well as safety and efficacy data in accordance with the guidelines for the preplanned analyses, including data pertaining to monitoring of AML progression outlined in the DMC charter. An independent third party will prepare the reports of aggregate data summaries and individual subject data listings, as appropriate, to the DMC members for each scheduled meeting.

The DMC responsibilities, authorities, and procedures will be detailed in the DMC charter, which will be endorsed by the DMC prior to the first data review meeting. Operational details for the DMC will be detailed in the DMC charter.

9.10.5 Steering Committee

A SC will be established by charter for this study. The Steering Committee will be comprised of study investigators, sponsor representatives, and may include additional ad hoc members. The SC will serve in an advisory capacity to the sponsor. Operational details for the SC will be detailed in a separate SC charter.

Note: The SC is separate from the DMC.

9.10.6 Exploratory Analysis

Descriptive statistics will also be provided for exploratory parameters (eg, GDF11, SF3B1, c-reactive protein, SARS-CoV-2 antibody, and other molecular markers). Statistical test will be applied for these parameters if applicable. Full details will be included in the SAP.

9.10.7 Subgroup Analysis

Appropriate subgroup analyses by stratification factors and other baseline characteristics for clinical activity may be conducted as exploratory analyses. Full details will be included in the SAP.

10 ADVERSE EVENTS

10.1 Monitoring, Recording and Reporting of Adverse Events

An AE is any noxious, unintended, or untoward medical occurrence that may appear or worsen in a subject during the course of a study. It may be a new intercurrent illness, a worsening concomitant illness, an injury, or any concomitant impairment of the subject's health, including laboratory test values (as specified by the criteria in [Section 10.3](#)), regardless of etiology. Any worsening (ie, any clinically significant adverse change in the frequency or intensity of a pre-existing condition) should be considered an AE. A diagnosis or syndrome should be recorded on the AE page of the eCRF rather than the individual signs or symptoms of the diagnosis or syndrome.

Abuse, withdrawal, sensitivity or toxicity to an investigational product should be reported as an AE. Overdose, accidental or intentional, whether or not it is associated with an AE should be reported on the overdose eCRF (See [Section 7.2.3](#) for the definition of overdose). Any sequela of an accidental or intentional overdose of an investigational product should be reported as an AE on the AE eCRF. If the sequela of an overdose is an SAE, then the sequela must be reported on an SAE report form and on the AE eCRF. The overdose resulting in the SAE should be identified as the cause of the event on the SAE report form and eCRF but should not be reported as an SAE itself.

In the event of overdose, the subject should be monitored as appropriate and should receive supportive measures as necessary.

- Luspatercept: There is no known specific antidote for luspatercept overdose. Actual treatment should depend on the severity of the clinical situation and the judgment and experience of the treating physician. Phlebotomy may be performed if excessively high hemoglobin levels occur.
- Epoetin alfa: The therapeutic margin of epoetin alfa is very wide. Overdosage of epoetin alfa may produce effects that are extensions of the pharmacological effects of the hormone. Phlebotomy may be performed if excessively high hemoglobin levels occur. Additional supportive care should be provided as necessary.

All subjects will be monitored for AEs during the study. Assessments may include monitoring of any or all of the following parameters: the subject's clinical symptoms, laboratory, pathological, radiological or surgical findings, physical examination findings, or findings from other tests and/or procedures.

All AEs will be recorded by the investigator from the time the subject signs informed consent until 42 days after the last dose of IP as well as those SAEs made known to the investigator at any time thereafter that are suspected of being related to IP. Adverse events (AEs) and SAEs will be recorded on the AE page of the eCRF and in the subject's source documents. All SAEs must be reported to Celgene Drug Safety within 24 hours of the investigator's knowledge of the event by facsimile, or other appropriate method.

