ECOG Performance Status	6.1.7	X	X	-	-	-	X	X	X	X	-	-	-
Urinalysis	6.1.13	X	X	-	-	-	Every 12 weeks ie, W13D1 W25D1 etc.	-	-	-	-	-	-
ECG (12-lead)	6.1.8	X	-	-	-	-	-	-	-	-	-	-	-
Pregnancy Test and Counseling ⁱ	6.1.14	X	X	-	-	-	X	-	-	X	X	X ^k	-
Adverse events	6.1.18 10	Continuous, after signing informed consent until 42 days after last IP administration										-	-

Table 3: Table of Events

	Section	Screening Day -35 to Random-ization	Treatment Period (open-label)								Post-treatment Follow-up		
			W1D1 Visit ^c	W2D1 Visit	W3D1 Visit	Add. Visits EPO W5/6D1 W8/9D1 etc.	3-wkly Visits W4D1 W7D1 W10D1 etc.	Efficacy Assessment Independent of any dose delays		EOT Visit ^a	42-Day Follow-up	Long Term Follow-up	End of Study
								24-Wk MDS Assessment Visit D169	Every 24 wks D337 D505 etc.				
Section								6.4	6.4	6.2.2/11.1	6.3.1	6.3.2	11.2
Time window				±2 days	±2 days	±2 days	±2 days	±14 days ^b	±14 days ^b		+3 days	±7 days	
Prior and Concomitant medications/ procedures	6.1.17 8	Continuous, 8 weeks prior to randomization until 42 days after last IP administration or until the EOT visit, whichever occurs later									-	-	
Vital Signs (Height to be measured only at screening)	6.1.6	X	X	X	X	X ^d blood pressure only	X	X	X	X	-	-	-
Serum Chemistry	6.1.10	X	X	-	-	-	X	X	X	X	-	-	-
EFFICACY ASSESSMENTS													
Hematology	6.1.9	X	X	X	X	X ^d local Hgb only	X	X	X	X	-	-	-
Serum EPO	6.1.11	X	-	-	-	-	Every 6 weeks, ie, W7D1 W13D1 etc.	X	X	X	-	-	-
Serum Ferritin and other iron-related markers	6.1.12	X	X	-	-	-	X	X	X	X	-	-	-

Table 3: Table of Events

	Section	Screening Day -35 to Random-ization	Treatment Period (open-label)								Post-treatment Follow-up		
			W1D1 Visit ^c	W2D1 Visit	W3D1 Visit	Add. Visits EPO W5/6D1 W8/9D1 etc.	3-wkly Visits W4D1 W7D1 W10D1 etc.	24-Wk MDS Assessment Visit D169	Every 24 wks D337 D505 etc.	EOT Visit ^a	42-Day Follow-up	Long Term Follow-up	End of Study
Section								6.4	6.4	6.2.2/11.1	6.3.1	6.3.2	11.2
Time window				±2 days	±2 days	±2 days	±2 days	±14 days ^b	±14 days ^b		+3 days	±7 days	

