			W1D1 Visit ^c	W2D1 Visit	W3D1 Visit	Add. Visits EPO W5/6D1 W8/9D1 etc.	3-wkly Visits W4D1 W7D1 W10D1 etc.	Efficacy Assessment Independent of any dose delays		EOT Visit ^a	42-Day Follow-up	Long Term Follow-up	End of Study	
								24-Wk MDS Assessment Visit D169	Every 24 wks D337 D505 etc.					
Section								6.4	6.4	6.2.2/11.1	6.3.1	6.3.2	11.2	
Time window				±2 days	±2 days	±2 days	±2 days	±14 days ^b	±14 days ^b		+3 days	±7 days		
ADA Sample Collection (Luspatercept arm only) Should be collected prior to IP dosing on a dosing day	6.6	–	X	–	–	–	–	W4D1 W10D1 W16D1 W22D1 only	X	And every 12 weeks (±14 days) from the 24-Week MDS Assessment visit for up to one year from the first dose. If the subject was discontinued from study treatment earlier than one year from the first dose, additional samples will be collected if last ADA is positive.			–	
QUALITY-OF-LIFE														
EORTC QLQ-C30 ^g	6.8	X	X	–	–	–	–	X 6-wkly only W7D1 W13D1 etc.	X	X D337 only	X	–	–	–
FACT-An ^g	6.8	X	X	X	X	–	–	X	X	X D337 only	X	–	–	–
QUALMS-p ^g	6.8	X	–	–	–	–	–	–	X	–	–	–	–	–

Table 3: Table of Events

	Section	Screening Day -35 to Random-ization	Treatment Period (open-label)								Post-treatment Follow-up		
			W1D1 Visit ^c	W2D1 Visit	W3D1 Visit	Add. Visits EPO W5/6D1 W8/9D1 etc.	3-wkly Visits W4D1 W7D1 W10D1 etc.	Efficacy Assessment Independent of any dose delays	24-Wk MDS Assessment Visit D169	Every 24 wks D337 D505 etc.	EOT Visit ^a	42-Day Follow-up	Long Term Follow-up
Section								6.4	6.4	6.2.2/11.1	6.3.1	6.3.2	11.2
Time window				±2 days	±2 days	±2 days	±2 days	±14 days ^b	±14 days ^b		+3 days	±7 days	
Patient Treatment Satisfaction Survey ^g	6.8	X	X	-	-	-	6-wkly only W7D1 W13D1 etc.	X	X D337 only	X	-	-	-
Healthcare Resource Utilization	6.9	After signing ICF and until 42 days after the last IP dose or End of Treatment Visit, whichever period is longer									-	-	
FOLLOW-UP													
Monitoring for progression to AML and other malignancies/pre-malignancies	6.1.19 6.3.2 10.5	After signing ICF and until 5 years from the first dose of IP, or 3 years from the last dose (whichever occurs later), or until death, lost to follow-up, withdrawal of consent for further data collection											
Post-treatment MDS therapies	6.3.2	-	-	-	-	-	-	-	-	-	X	X	X
Survival Follow-up	6.3.2	-	-	-	-	-	-	-	-	-	X	X	X

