6.3 Post-treatment Follow-up Period

6.3.1 Safety Follow-up (42-Day Follow-up)

All subjects will be followed for 42 days after the last dose of IP for AE reporting, as well as SAEs made known to the investigator at any time thereafter that are suspected of being related to IP, as described in [Section 10.1](#).

Refer to [Table 3](#) for additional assessments to be performed at the 42-Day Follow-up. An administrative time window of +3 days is permitted.

Females of childbearing potential should avoid becoming pregnant for 12 weeks after the last dose of IP and male subjects should avoid fathering a child for 12 weeks after the last dose of IP. Refer to [Section 10.4](#) for additional details.

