^c If dose delay is > 12 consecutive weeks, treatment should be discontinued

^d Predose Hgb value not being influenced by RBC transfusion (ie, Hgb result > 14 days after last RBC transfusion or within 3 days from next RBC transfusion); Hgb should be rechecked weekly during dose delay.

^e Upper limit of normal $> 10,000$ total WBC/ μ L or as defined by institutional standards.

^f Peripheral blood smear should be prepared for central pathology lab assessment.

^g At the investigator's discretion, bone marrow samples may also be collected and analyzed centrally to assess MDS disease status (eg, cytomorphology) prior to making decision regarding treatment discontinuation. The central laboratory must also confirm < 5% bone marrow blasts prior to resumption of treatment.

^h The investigator may contact the Medical Monitor prior to making decision regarding treatment discontinuation.

ⁱ Thrombocytopenia, leukopenia, and neutropenia toxicity grades as defined by CTCAE criteria.

^k Every attempt should be taken to assess the blasts count in peripheral blood prior to dosing, however, in circumstances where results are not readily available at the time of planned dosing, the investigator may proceed with dosing provided there are no signs of clinical progression. In this case, results must be evaluated as soon as they become available (but no later than 3 days post dosing). If presence of $\geq 1\%$ blasts in peripheral blood is observed, actions described in table above must be followed immediately.

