10.8 COVID-19 Reporting

The occurrence of a COVID-19 event will be monitored as part of the assessment of AEs throughout the course of the study. Investigators are to report the occurrence of COVID-19 events, regardless of casual relationship to IP, occurring at any time for the duration of treatment up to 42 days after the last dose.

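### For subjects stopped after a dose delay of more than 12 weeks, the adverse event window closes at least about 6 to 9 weeks before the End of Treatment visit

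*Combined protocol and SAP*

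**What the plan says.** **AE window.** Section 10.1 sets it as "from the time the subject signs informed consent until 42 days after the last dose of IP" and adds an open-ended exception: "as well as those SAEs made known to the investigator at any time thereafter that are suspected of being related to IP". Section 10.6 applies the same limits to serious AEs (SAEs). The Table 3 row for AEs reads "Continuous, after signing informed consent until 42 days after last IP administration", and Section 6.3.1 says "All subjects will be followed for 42 days after the last dose of IP for AE reporting". For COVID-19 events, Section 10.8 has "occurring at any time for the duration of treatment up to 42 days after the last dose". None of these mentions the EOT visit.

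**Stopping after a delay.** Under footnote c of Tables 5 and 7, once a delay exceeds 12 "consecutive weeks, treatment should be discontinued". Section 6.2.2 ties the EOT visit to the decision to stop, not to the last dose.

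**Other data in the same period.** Table 3 collects concomitant medication and procedures as follows: "Continuous, 8 weeks prior to randomization until 42 days after last IP administration or until the EOT visit, whichever occurs later". For healthcare resource use it has "After signing ICF and until 42 days after the last IP dose or End of Treatment Visit, whichever period is longer". Transfusions (Table 3, Section 6.4.1) run to 8 weeks after the last dose or to EOT, whichever is later. Section 8, however, ends concomitant medication at 42 days after the last dose and does not mention EOT.

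**Related text.** Section 6.2 lists AE assessment as a continuing activity in the Treatment Period and refers to Section 10 for the detail. Section 6.1.5 requires significant physical examination findings to be reported as AEs, and Table 3 schedules a physical examination at EOT. Table 2 gives safety two timeframes: one ending 42 days after the last dose, the other running from randomization through Week 48.

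**The concern.** The AE window is anchored to a date that, for a subject on hold, is known only in hindsight. If dosing never resumes, the last dose turns out to lie well over 42 days back, and the window has closed while the subject was still in the Treatment Period.

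The subjects concerned are on hold for suspected related Grade 3 or higher AEs or, under Table 5, for worsening cytopenias. Their later course is of safety interest. A new drug or a hospital stay in that interval would be collected under Table 3, while the event behind it need not be entered as an AE. Whether an SAE is suspected to be related decides whether it must be recorded, and in this open-label trial the investigator makes that judgement knowing the treatment.

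There is also a visit problem. The 42-Day Follow-up has a window of +3 days, and footnote a of Table 3 deals only with discontinuation within 7 days either side of it. A stop decision taken weeks later is not covered.

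**Working it through.** The plan states no figure for this gap, so there is none to reproduce. The check is date arithmetic.

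**Inputs**
- AE window after the last dose: 42 days (Sections 10.1, 10.6, 6.3.1; Table 3).
- Delay that triggers stopping: more than 12 weeks, that is, more than 12 × 7 = 84 days (footnote c, Tables 5 and 7).
- Dosing interval: 21 days for luspatercept (Section 7.2.1.1), 7 days for epoetin alfa (Section 7.2.2.1).
- Start of the delay: not defined, so both readings are shown.

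**Formulas**
- Time from last dose to stop decision = offset + 84. The offset is the dosing interval if the delay is counted from the missed dose, and 0 if it is counted from the last dose.
- Gap = time from last dose to stop decision − 42.

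| Arm | Delay counted from | Last dose to stop (days) | Gap (days) | Gap (weeks) |
|---|---|---|---|---|
| Luspatercept | missed dose | > 21 + 84 = 105 | > 105 − 42 = 63 | > 9 |
| Epoetin alfa | missed dose | > 7 + 84 = 91 | > 91 − 42 = 49 | > 7 |
| Either | last dose | > 84 | > 84 − 42 = 42 | > 6 |

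These are minimum gaps for a subject stopped under footnote c, because EOT follows the decision. If the physician stops treatment sooner, the gap is shorter, and it vanishes when EOT falls within 42 days of the last dose. If dosing resumes, the last dose moves later and every event in the delay falls inside the window.

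**What the interval still captures**
- Suspected-related SAEs, without time limit (Section 10.1).
- Malignancy, pre-malignancy and AML, regardless of causality (Sections 6.1.19 and 10.5).
- Date and cause of death (Section 6.3.2).
- Hospitalizations with their reason (Section 6.9 and Table 3).
- Follow-up of SAEs that began earlier and are unresolved (Section 10.2.6).

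What remains uncovered is non-serious AEs, and SAEs not suspected to be related other than malignancy or AML.

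**With the window extended to EOT**, the gap before EOT is 0 in both arms.

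**The case against.** The strongest reply is that sites cannot know during a hold which dose was the last. Section 6.2 calls for continuing AE assessment in the Treatment Period and Section 10.1 for monitoring throughout the study, so a careful site keeps recording. This stands against a stronger reading that a reader might infer, namely that these data will go unrecorded. The documents do not show that. They show only that the recording rule does not require the entries. Section 6.2 refers back to Section 10 for its detail, so it does not by itself lengthen the window.

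Three other inferences also go too far:

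- **That AE collection ends entirely at 42 days.** The exception for suspected-related SAEs is in the same sentence of Section 10.1, and the second safety timeframe in Table 2 is unexplained. The COVID-19 wording in Section 10.8 covers the duration of treatment and does not clearly exclude a delay.
- **That holds without footnote c leave an unlimited gap.** The white cell and blast rows have their own stop-or-resume rules. A hemoglobin hold normally ends in redosing, which moves the last dose later. Only a subject whose hemoglobin never falls to the restart level would have no stated limit.
- **That the gap biases the comparison between arms.** A 63 versus 49 day difference arises only if the delay is counted from the missed dose. The current window treats the arms alike relative to last exposure, whereas running it to EOT would give 105 versus 91 days, 14 days apart. That is a fair point in favor of the fixed window, and any change has to preserve the 42-day comparison.

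A fixed window anchored to exposure is a legitimate choice. What is left is an inconsistency with the other Table 3 rows and with the examination findings due at EOT.

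**Conclusion.** The point holds in a limited form. For subjects stopped after a delay of more than 12 weeks who never restart, the written AE window closes at least about 6 to 9 weeks before EOT. Over that time the rule does not require recording of non-serious AEs, or of SAEs judged not related other than malignancy or AML.

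The range depends on where the delay is taken to start, which the protocol does not define, and on the stop being made under footnote c and not sooner. The number of such subjects is not given, so the effect on the safety tables cannot be sized. Nothing here touches the primary or key secondary efficacy endpoints. The change is worth making because it is cheap and reuses a clause that Table 3 already contains.

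**What to change.** - In Sections 10.1, 10.6, 10.8 and 6.3.1 and in the AE row of Table 3, end the AE, SAE and COVID-19 window at the later of 42 days after the last dose and the EOT visit. Keep the existing exception for suspected-related SAEs.
- Reconcile Section 8 with the Table 3 row for concomitant medication, and clarify the second safety timeframe in Table 2.
- State that the 42-Day Follow-up is done at the EOT visit when the stop decision falls more than 42 days after the last dose.
- Flag events that start more than 42 days after the last dose and tabulate them separately, so that the exposure-anchored 42-day comparison between arms stays as it is.

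No dosing or stopping rule changes. The cost is protocol wording, an adjusted eCRF window and edit check, and a few more AE records at a visit that already takes place. The drawback is that the added records are off-drug and their follow-up length may differ by arm, which the flag handles.

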10.2 Evaluation of Adverse Events

A qualified investigator will evaluate all adverse events as to:

10.2.1 Seriousness

An SAE is any AE occurring at any dose that:

- Results in death;
- Is life-threatening (ie, in the opinion of the investigator, the subject is at immediate risk of death from the AE);
- Requires inpatient hospitalization or prolongation of existing hospitalization (hospitalization is defined as an inpatient admission, regardless of length of stay);
- Results in persistent or significant disability/incapacity (a substantial disruption of the subject's ability to conduct normal life functions);
- Is a congenital anomaly/birth defect;
- Constitutes an important medical event.

Important medical events are defined as those occurrences that may not be immediately life-threatening or result in death, hospitalization, or disability, but may jeopardize the subject or require medical or surgical intervention to prevent one of the other outcomes listed above. Medical and scientific judgment should be exercised in deciding whether such an AE should be considered serious.

Events **not considered** to be SAEs are hospitalizations for:

- a standard procedure for protocol therapy administration. However, hospitalization or prolonged hospitalization for a complication of therapy administration will be reported as an SAE.
- routine treatment or monitoring of the studied indication not associated with any deterioration in condition.
- the administration of blood or platelet transfusion as routine treatment of studied indication. However, hospitalization or prolonged hospitalization for a complication of such transfusion remains a reportable SAE.
- a procedure for protocol/disease-related investigations (eg, surgery, scans, endoscopy, sampling for laboratory tests, bone marrow sampling). However, hospitalization or prolonged hospitalization for a complication of such procedures remains a reportable SAE.
- hospitalization or prolongation of hospitalization for technical, practical, or social reasons, in absence of an AE.
- a procedure that is planned (ie, planned prior to start of treatment on study); must be documented in the source document and the eCRF. Hospitalization or prolonged hospitalization for a complication remains a reportable SAE.
- an elective treatment of or an elective procedure for a pre-existing condition, unrelated to the studied indication, that has not worsened from baseline.

- emergency outpatient treatment or observation that does not result in admission, unless fulfilling other seriousness criteria above.

If an AE is considered serious, both the AE page/screen of the eCRF and the SAE Report Form must be completed.

For each SAE, the investigator will provide information on severity, start and stop dates, relationship to the IP, action taken regarding the IP, and outcome.

10.2.2 Severity/Intensity

For both AEs and SAEs, the investigator must assess the severity/ intensity of the event.

The severity/intensity of AEs will be graded based upon the subject's symptoms according to the current active minor version of the Common Terminology Criteria for Adverse Events (CTCAE, Version 4.0); http://ctep.cancer.gov/protocolDevelopment/electronic_applications/ctc.htm#ctc_40

AEs that are not defined in the CTCAE should be evaluated for severity/intensity according to the following scale:

- Grade 1 = Mild – transient or mild discomfort; no limitation in activity; no medical intervention/therapy required
- Grade 2 = Moderate – mild to moderate limitation in activity, some assistance may be needed; no or minimal medical intervention/therapy required
- Grade 3 = Severe – marked limitation in activity, some assistance usually required; medical intervention/therapy required, hospitalization is possible
- Grade 4 = Life-threatening – extreme limitation in activity, significant assistance required; significant medical intervention/therapy required, hospitalization or hospice care probable
- Grade 5 = Death - the event results in death

The term “severe” is often used to describe the intensity of a specific event (as in mild, moderate or severe myocardial infarction); the event itself, however, may be of relatively minor medical significance (such as severe headache). This criterion is *not* the same as “serious” which is based on subject/event *outcome* or *action* criteria associated with events that pose a threat to a subject's life or functioning.

Seriousness, not severity, serves as a guide for defining regulatory obligations.

